[figure not shown]

[figure not shown]

Clinical Trial Protocol

Document Number:		c32357152-03
EudraCT No. EU Trial No.	2020-003097-46	
BI Trial No.	1407-0038	
BI Investigational Medicinal Product	BI 730357	
Title	The effect of BI 730357 on the pharmacokinetics of rosuvastatin, digoxin, metformin and furosemide given as a cocktail – an open-label, non-randomised, 2-period fixed-sequence trial in healthy subjects	
Lay Title	A study in healthy people to test whether BI 730357 affects how 4 other medicines (rosuvastatin, digoxin, metformin, and furosemide) are taken up in the body	
Clinical Phase	I	
Clinical Trial Leader	 Phone:  Fax: 	
Principal Investigator	 Phone:  , Fax: 	
Status	Final Protocol (Revised Protocol (based on global amendment 2))	
Version and Date	Version: 3.0	Date: 19 October 2020
Page 1 of 82		
Proprietary confidential information © 2020 Boehringer Ingelheim International GmbH or one or more of its affiliated companies. All rights reserved. This document may not - in full or in part - be passed on, reproduced, published or otherwise used without prior written permission		

CLINICAL TRIAL PROTOCOL SYNOPSIS

Company name	Boehringer Ingelheim
Protocol date	30 July 2020
Revision date	19 October 2020
BI trial number	1407-0038
Title of trial	The effect of BI 730357 on the pharmacokinetics of rosuvastatin, digoxin, metformin and furosemide given as a cocktail – an open-label, non-randomised, 2-period fixed-sequence trial in healthy subjects
Principal Investigator	[REDACTED]
Trial site	[REDACTED]
Clinical phase	I
Trial rationale	Evaluation of in-vivo effects of BI 730357 on drug transporter probe substrates
Trial objective	To assess the effect of multiple oral doses of BI 730357 on the pharmacokinetics of rosuvastatin, digoxin, metformin and furosemide given as a cocktail
Trial design	Non-randomised, open-label, 2-period fixed-sequence design
Trial endpoints:	Primary endpoints: AUC _{0-∞} and C _{max} of rosuvastatin, digoxin, metformin and furosemide Secondary endpoints: AUC _{0-tz} of rosuvastatin, digoxin, metformin and furosemide
Number of subjects	
total entered	15
each treatment	15
Diagnosis	Not applicable
Main criteria for inclusion	Healthy male and female subjects, age of 18 to 55 years (inclusive), body mass index (BMI) of 18.5 to 29.9 kg/m ² (inclusive)
Trial product 1	CRESTOR [®] 10 mg film-coated tablets (rosuvastatin)
Dose	1 x 1 tablet (10 mg rosuvastatin)
mode of admin.	Oral with 280 mL of water after a standardized breakfast
Trial product 2	Lenoxin [®] 0.25 mg tablets (digoxin)
Dose	1 x 1 tablet (0.25 mg digoxin)
mode of admin.	Oral with 280 mL of water after a standardized breakfast

Trial product 3 Dose mode of admin.	MetfoLiquid GeriaSan [®] , 1000 mg / 5 mL oral solution (metformin) 1 x 0.05 mL oral solution (10 mg metformin) Oral with 280 mL of water after a standardized breakfast
Trial product 4 Dose mode of admin.	Lasix [®] liquidum 10 mg/mL oral solution (furosemide) 1 x 0.1 mL oral solution (1 mg furosemide) Oral with 280 mL of water after a standardized breakfast
Trial product 5 Dose mode of admin.	BI 730357, 100 mg tablets 2 x 3 tablets daily (= 600 mg BI 730357 per day) during treatment Test only Oral with 240 mL of water after a standardized meal
Duration of treatment	Rosuvastatin, digoxin, metformin and furosemide are given always together as a cocktail (the cocktail). The cocktail will be given single dose in both trial periods. Treatment Reference: the cocktail Treatment Test: 3 tablets BI 730357 bid on study days -7 until study day 6 (total of 13 dosing days); on study day 1 the cocktail will be administered 1 hour after the morning dose of BI 730357 
Statistical methods	The effect of BI 730357 on the pharmacokinetics of each of the cocktail components rosuvastatin, digoxin, metformin and furosemide will be estimated based on the ratio (test to reference) of the geometric means (gMeans) of the primary and secondary endpoints. Additionally, their two-sided 90% confidence intervals (CIs) will be provided. This method corresponds to the two one-sided t-tests procedure, each at the 5% significance level. Since the main focus is on estimation and not testing, an acceptance range was not specified. The statistical model will be an analysis of variance (ANOVA) on the logarithmic scale including effects for 'subject' and 'treatment'. CIs will be calculated based on the residual error from the ANOVA. Descriptive statistics will be calculated for all endpoints.

FLOW CHART – TREATMENT REFERENCE

Period	Visit	Day	Planned time (relative to cocktail administration) [h:min]	Approximate clock time of actual day [h:min]	Event and comment	Safety laboratory ⁷	PK blood, cocktail components	PK urine, cocktail components ^{6,8}	12-lead ECG	Vital signs (BP, PR)	Questioning for AEs and concomitant therapy ⁵	
SCR	1	-21 to -2			Screening (SCR) ¹	A			x	x	x	
1	2	-1	-13:00	20:00	Admission to trial site	x ⁴					x	
		1	-2:00	07:00			x ²	x ²	x ²	x ²	x ²	
			-1:30	07:30	Standardized breakfast							
			0:00	09:00	Cocktail dosing				▲			x
			0:20	09:20				x				
			0:40	09:40				x				
			1:00	10:00				x		x	x	x
			1:30	10:30				x				
			2:00	11:00	240 mL fluid intake			x		x	x	x
			2:30	11:30				x				
			3:00	12:00				x				
			4:00	13:00	240 mL fluid intake, thereafter lunch ³			x	+	x	x	x
			5:00	14:00				x				
			6:00	15:00				x				
			8:00	17:00	Extended snack ³ (voluntary)			x	+			x
			10:00	19:00				x				
			10:30	19:30	Standardized dinner							
			12:00	21:00				x	+			x
			2	24:00	09:00	Breakfast ³	B	x	+	x	x	x
				28:00	13:00	Lunch						x
		32:00	17:00	Snack (voluntary)								
		34:30	19:30	Dinner								
		36:00	21:00			x	+			x		
	3	48:00	09:00	Discharge, breakfast (voluntary) ³		x	▼			x		
	4	71:00	08:00	Ambulatory visit		x				x		
	5	95:00	08:00	Ambulatory visit		x				x		
	7	143:00	08:00	Ambulatory visit		x				x		

- Subject must be informed and written informed consent obtained prior to starting any screening procedures. Screening procedures include physical examination, check of vital signs, ECG (including rhythm stripe over 15 min), safety laboratory (including drug screening), demographics (including determination of body height and weight, smoking status and alcohol history), pregnancy test in females, relevant medical history, concomitant therapy and review of inclusion/exclusion criteria. Pharmacogenetic samples will be collected if needed.
- The time is approximate; the procedure is to be performed and completed within 3 h prior to study drug administration.
- If several actions are indicated at the same time point, the intake of meals will be the last action.
- Only urine drug screening, alcohol breath test and pregnancy test in females.
- AEs and concomitant therapies will be recorded throughout the trial, but will be specifically asked for at the time points indicated in the Flow Chart above.
- A blank urine sample (x) is to be obtained prior to administration of trial medication. Other urine samples are to be collected over the stated post-dose intervals (◀—|—|—▶) 0-4, 4-8, 8-12, 12-24, 24-36 and 36-48 h.
- Letters A and B define different sets of safety laboratory examinations (for details refer to Section 5.2.3).

FLOW CHART – TREATMENT TEST

Period	Visit	Day	Planned time (relative to cocktail administration) [h:min]	Approx. clock time of actual day [h:min]	Event and comment	Safety laboratory ⁹	PK _{blood, cocktail components}	PK _{blood, BI 730357}	PK _{urine, cocktail components 7, 10}	12-lead ECG	Vital signs (BP, PR)	Questioning for AEs and concomitant therapy ⁶		
2	3	-7	-170:30	06:30	Ambulatory visit, standardized breakfast	X ⁵				X	X			
			-170:00	07:00	Dosing BI 730357	B						X		
			-158:30	18:30	Ambulatory visit, standardized dinner									
		-6	-158:00	19:00	Dosing BI 730357								X	
			-146:30	06:30	Ambulatory visit, standardized breakfast									
			-146:00	07:00	Dosing BI 730357								X	
		-5	-134:30	18:30	Ambulatory visit, standardized dinner									
			-134:00	19:00	Dosing BI 730357								X	
			-122:30	06:30	Ambulatory visit, standardized breakfast									
		-4	-122:00	07:00	Dosing BI 730357								X	
			-110:30	18:30	Ambulatory visit, standardized dinner									
			-110:00	19:00	Dosing BI 730357								X	
		-3	-98:30	06:30	Ambulatory visit, standardized breakfast									
			-98:00	07:00	Dosing BI 730357								X	
			-86:30	18:30	Ambulatory visit, standardized dinner									
		-2	-86:00	19:00	Dosing BI 730357								X	
			-74:30	06:30	Ambulatory visit, standardized breakfast						X	X		
			-74:00	07:00	Dosing BI 730357	B							X	
		-1	-62:30	18:30	Ambulatory visit, standardized dinner									
			-62:00	19:00	Dosing BI 730357								X	
			-50:30	06:30	Ambulatory visit, standardized breakfast									
		1	-50:00	07:00	Dosing BI 730357								X	
			-38:30	18:30	Ambulatory visit, standardized dinner									
			-38:00	19:00	Dosing BI 730357								X	
1	3	-1	-26:30	06:30	Ambulatory visit, standardized breakfast									
			-26:00	07:00	Dosing BI 730357							X		
			-14:00	19:00	Admission to trial site	X ⁵							X	
			-13:30	19:30	Standardized dinner									
		1	-13:00	20:00	Dosing BI 730357				X ⁸					X
			-2:00	07:00				X ²		X ²	X ²	X ²	X ²	X ²
			-1:30	07:30	Standardized breakfast									
			-1:00	08:00	Dosing BI 730357				X ⁸					X
			0:00	09:00	Cocktail dosing						▲			X
			0:20	09:20				X						
			0:40	09:40				X						
			1:00	10:00				X				X	X	X
			1:30	10:30				X						
			2:00	11:00	240 mL fluid intake			X				X	X	X
			2:30	11:30				X						
			3:00	12:00				X						
			4:00	13:00	240 mL fluid intake, thereafter lunch ³			X			+	X	X	X
			5:00	14:00				X						
			6:00	15:00				X						
			8:00	17:00	Extended snack ³ (voluntary)			X			+	X	X	X
			10:00	19:00				X						
			10:30	19:30	Standardized dinner									
			11:00	20:00	Dosing BI 730357					X ⁸				X
			12:00	21:00				X			+			X

[figure not shown]
FLOW CHART – Treatment Test, continued

Period	Visit	Day	Planned time (relative to cocktail administration) [h:min]	Approximate clock time of actual day [h:min]	Event and comment	Safety laboratory ⁹	PK blood, cocktail components	PK blood, BI 730357	PK urine, cocktail components ^{7, 10}	12-lead ECG	Vital signs (BP, PR)	Questioning for AEs and concomitant therapy ⁶		
2	3	2	22:30	07:30	Standardized breakfast									
			23:00	08:00	Dosing BI 730357			x ⁸					x	
			24:00	09:00		B	x		+	x	x	x		
			28:00	13:00	Lunch									x
			32:00	17:00	Extended snack ³ (voluntary)									
			34:30	19:30	Standardized dinner									
			35:00	20:00	Dosing BI 730357									x
			36:00	21:00			x		+					x
		3	46:30	07:30	Standardized breakfast									
			47:00	08:00	Dosing BI 730357									x
			48:00	09:00	Discharge		x		▼					x
			58:00	19:00	Ambulatory visit, standardized dinner									x
		4	58:30	19:30	Dosing BI 730357									x
			70:00	07:00	Ambulatory visit, standardized breakfast									
			70:30	07:30	Dosing BI 730357									x
			71:00	08:00			x							
			82:00	19:00	Ambulatory visit, standardized dinner									
		5	82:30	19:30	Dosing BI 730357									x
			94:00	07:00	Ambulatory visit, standardized breakfast									
			94:30	07:30	Dosing BI 730357									x
			95:00	08:00		B	x					x		
			106:00	19:00	Ambulatory visit, standardized dinner									
			106:30	19:30	Dosing BI 730357									x
		6	118:00	07:00	Ambulatory visit, standardized breakfast									
			118:30	07:30	Dosing BI 730357									x
			119:00	08:00			x							
			130:00	19:00	Ambulatory visit, standardized dinner									
			130:30	19:30	Dosing BI 730357									x
8	167:00	08:00	Ambulatory visit		x						x			
FU	4	14-22			End of trial (EoTrial) examination ⁴	C			x	x	x			

- [For footnote 1 see [Flow Chart of Treatment Reference](#)]
- The time is approximate; the procedure is to be performed and completed within 3 h prior to first drug administration.
- If several actions are indicated at the same time point, the intake of meals will be the last action.
- End of trial examination includes physical examination, vital signs, ECG, safety laboratory, pregnancy test in females, recording of AEs and concomitant therapies.
- Only urine drug screening, alcohol breath test and pregnancy test in females

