5.2.5.2 Adverse event collection and reporting

5.2.5.2.1 AE collection

Upon enrolment into a trial, the subject's baseline condition is assessed (for instance, by documentation of medical history/concomitant diagnoses), and relevant changes from baseline are noted subsequently.

Subjects will be required to report spontaneously any AEs as well as the time of onset, end time, and intensity of these events. In addition, each subject will be regularly assessed by the medical staff throughout the clinical trial and whenever the investigator deems necessary. As a minimum, subjects will be questioned for AEs (and concomitant therapies) at the time points indicated in the [Flow Chart](#). Assessment will be made using non-specific questions such as ‘How do you feel?’. Specific questions will be asked wherever necessary in order to more precisely describe an AE.

A carefully written record of all AEs shall be kept by the investigator in charge of the trial. Records of AEs shall include data on the time of onset, end time, intensity of the event, and any treatment or action required for the event and its outcome.

The following must be collected and documented on the appropriate CRF(s) by the investigator:

- From signing the informed consent onwards until an individual subject’s end of trial:
 - All AEs (serious and non-serious) and all AESIs
 - The only exception to this rule are AEs (serious and non-serious) and AESIs in Phase I trials in healthy volunteers, when subjects discontinue from the trial due to screening failures prior to administration of any trial medication. In these cases, the subjects’ data must be collected at trial site but will not be entered in the CRF or trial database and will not be reported in the CTR.
- After the individual subject’s end of trial:
 - The investigator does not need to actively monitor the subject for AEs but should only report any occurrence of cancer and related SAEs and related AESIs of which the investigator may become aware of by any means of communication, e.g. phone call. Those AEs should, however, not be reported in the CRF.

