7.3.4 Safety analyses

Safety will be analysed based on the assessments described in Section [2.2.2.2](#). All treated subjects (TS, refer to Section [7.2](#)) will be included in the safety analysis. Safety analyses will be descriptive in nature and based on BI standards. No hypothesis testing is planned.

For all analyses, the treatment actually administered (= treatment at onset of AE) to the subject will be used (any deviations from the planned treatment will be discussed in the minutes of the Report Planning Meeting).

Treatments will be compared in a descriptive way. Tabulations of frequencies/proportions will be used to evaluate categorical (qualitative) data, and tabulations of descriptive statistics will be used to analyse continuous (quantitative) data.

Measurements (such as ECG, vital signs, or laboratory parameters) or AEs will be assigned to treatments (see Section [4.1](#)) based on the actual treatment at the planned time of the measurement or on the recorded time of AE onset (concept of treatment emergent AEs). Therefore, measurements planned or AEs recorded prior to first intake of trial medication will be assigned to the screening period, those between trial medication intake and end of REP (see Section [1.2.3](#)) will be assigned to the treatment period. Events occurring after the REP but prior to next intake or end of trial termination date will be assigned to 'follow-up'. In case of two or more treatments, the follow-up will be summarized according to the previous treatment. These assignments including the corresponding time intervals will be defined in detail in the TSAP. Note that AEs occurring after the last per protocol contact but entered before final database lock will be reported to Pharmacovigilance only and will not be captured in the trial database.

Additionally, further treatment intervals (analysing treatments) may be defined in the TSAP in order to provide summary statistics for time intervals, such as combined treatments, on-treatment totals, or periods without treatment effects (such as screening and follow-up intervals).

Adverse events will be coded using the Medical Dictionary for Regulatory Activities (MedDRA). Frequency, severity, and causal relationship of AEs will be tabulated by treatment, system organ class, and preferred term. SAEs, AESIs (see Section [5.2.5.1](#)), and other significant AEs (according to ICH E3) will be listed separately.

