7.8.1 Adverse Events

AEs will be coded with the most recent version of MedDRA. The analysis of AEs will be descriptive in nature. All analyses of AEs will be based on the number of subjects with AEs and not on the number of AEs.

The analysis of AEs will be based on the concept of treatment emergent AEs. That means that all AEs occurring between first drug intake till last drug intake + REP will be assigned to the on-treatment phases as defined in Table [6.1:1](#). All AEs occurring before first drug intake will be assigned to 'screening' and all AEs occurring after the last drug intake and the REP will be assigned to 'follow-up'. For details on the treatment definition, see Section [6.1](#).

AEs will be analysed based on the actual treatment at the recorded time of AE onset. Any deviations from the planned treatment will be discussed in the minutes of the RPM.

Pre-defined adverse events of special interest (AESIs) are defined in the CTP Section 5.2.5.1.4. Hepatic injury, severe infections and opportunistic and mycobacterium tuberculosis infections are considered AESIs. The investigator classifies on the eCRF whether an observed AE was an AESI or not.

According to ICH E3 (3), in addition to Deaths and Serious Adverse Events and AESIs, 'other significant' AEs need to be listed in the clinical trial report. These will be any non-serious adverse event that led to an action taken with study drug (e.g. discontinuation or dose reduced or interrupted). SARS-CoV-2 infections and AEs related to SARS-CoV-2 will also be listed.

An overall summary of AEs will be presented.

The frequency of subjects with AEs will be summarised by treatment, primary system organ class (SOC) and preferred term. AEs which were considered by the investigator to be drug related (primary endpoint) will be summarised separately. A separate table will also be provided for subjects with serious adverse events (SAEs). A table will be provided for subjects with pre-specified AESIs, summarised by SOC and PT. The frequency of subjects with AEs will also be summarised by maximum intensity, primary SOC and preferred term.

The SOC will be sorted alphabetically, preferred terms will be sorted by frequency (within SOC).

Post-hoc AESIs may be defined at a later time point and summarised separately.

For further details on summarization of AE data, please refer to "Analysis and Presentation of Adverse Event Data from Clinical Trials" (4) and "Handling of missing and incomplete AE dates" (5).

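### Scheduled AE questioning and phase length both differ between Reference and Test, and the SAP compares AE frequencies by phase with neither a matched window nor a caveat

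*Protocol*

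**What the plan says.** The footnote on AE questioning is the same in both Flow Charts (Treatment Reference and Treatment Test): recording is continuous, but AEs and concomitant therapies "will be specifically asked for at the time points indicated in the Flow Chart above". Protocol 5.2.5.2.1 makes these questions a floor: "As a minimum, subjects will be questioned for AEs (and concomitant therapies) at the time points indicated in the" Flow Chart. The same section also requires subjects to report AEs on their own initiative, with onset time, end time and intensity.

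On analysis, protocol 7.3.4 states: "Treatments will be compared in a descriptive way". SAP 7.8.1 states: "The frequency of subjects with AEs will be summarised by treatment, primary system organ class (SOC) and preferred term", and the counting unit is the subject with an AE. SAP 6.1 and its Table 6.1:1 assign AEs by onset to four on-treatment phases: 'Cocktail', 'Cocktail + BI', 'BI' and 'BI + Cocktail'. 'Cocktail' ends 240 h after the first cocktail dose, or at the first BI 730357 dose if that is earlier. 'BI + Cocktail' runs from the second cocktail dose to 7 × 24 h after the last BI 730357 dose, or to trial termination if earlier. Neither document mentions that questioning or phase length differs between treatments.

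**The concern.** In Period 2 questioning is attached to the visits for supervised twice-daily dosing, so its density changes with treatment. Minor, short-lived complaints may be recalled less well the longer the wait before anyone asks. If so, the chance that an event is recorded depends on the phase in which it starts. The trial is open-label with a fixed sequence, so treatment, period and questioning schedule change together. With 15 subjects, one more or one fewer recorded subject moves a frequency by 1/15, or about 7 percentage points. A reader of the phase tables could take a difference between 'Cocktail' and 'BI + Cocktail' as a drug effect, and nothing in the plan warns that the columns were observed differently.

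**Working it through.** **Inputs from the Flow Charts (hours after the cocktail, AE-questioning column)**

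- Reference, 0 to 48 h: 0, 1, 2, 4, 8, 12, 24, 28, 36, 48 (10 marks, longest gap 12 h).
- Test, 0 to 48 h: 0, 1, 2, 4, 8, 11, 12, 23, 24, 28, 35, 36, 47, 48 (14 marks, longest gap 11 h).
- Reference, after 48 h: 71, 95, 143 (3 marks, longest gap 48 h).
- Test, after 48 h to 143 h: 58, 58.5, 70.5, 82.5, 94.5, 95, 106.5, 118.5, 130.5 (9 marks). The pairs 58/58.5 and 94.5/95 are half an hour apart, so these are 7 separate visits. The next mark is at 167 h, a gap of 36.5 h.
- Test, before the cocktail: 17 marks from -170 h to -1 h, 15 of them on Days -7 to -1. By onset these belong to 'BI' or 'Cocktail + BI', not to 'BI + Cocktail'.

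The Test mark at 95 h was read from extracted text. Without it the count is 8 and the visits are still 7.

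**Phase lengths (SAP Table 6.1:1)**

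- 'Cocktail': at most 10 × 24 = 240 h.
- 'BI + Cocktail': the last BI 730357 dose is at 130.5 h, so up to 130.5 + 168 = 298.5 h.
- After 167 h the next Test question is at the end-of-trial visit on Day 14 to 22, about 13 × 24 = 312 h to 21 × 24 = 504 h. So 298.5 − 167 = 131.5 h of 'BI + Cocktail' (44%) has no scheduled question.
- In Reference no question falls between 143 h and the first BI 730357 dosing visit, up to 240 − 143 = 97 h of the 'Cocktail' phase.

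**Delay from onset to next question, onset uniform over 48 to 143 h (95 h)**

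- Reference: (23² + 24² + 48²) / (2 × 95) = 3409 / 190 = 17.9 h.
- Test: [10² + 2 × 0.5² + 5 × 12² + 11.5² + (36.5² − 24²)] / (2 × 95) = 1709 / 190 = 9.0 h.

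**Illustration of capture.** The documents give no recall rate. Assume that the chance of an event being reported halves every *h* hours until the next question, so capture is the mean of 0.5^(delay/*h*), with *h* = 24, 48 or 96 h.

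| Onset window | *h* | Test | Reference | Test/Reference |
|---|---|---|---|---|
| 48 to 143 h | 24 | 79% | 63% | 1.26 |
| 48 to 143 h | 48 | 89% | 78% | 1.13 |
| 48 to 143 h | 96 | 94% | 88% | 1.06 |
| 0 to 48 h | 24 / 48 / 96 | | | 1.02 / 1.01 / 1.005 |

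Merging the paired marks into 7 visits gives 1.25, 1.13 and 1.06 for 48 to 143 h, so the ratio does not depend on counting 9 rather than 7.

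**Same model over the phases that the SAP tabulates.** The interval between the periods is not visible in the public text, so the first BI 730357 dose is varied, with the end-of-trial visit at 312 or 504 h.

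- First BI 730357 dose at 166 to 238 h after the first cocktail: capture ratio 0.61 to 0.94.
- At 262 to 310 h: 0.75 to 1.19. Still later starts take the upper end to about 1.3.

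The range falls on both sides of 1 because the long unasked stretch at the end of 'BI + Cocktail' offsets its dense first week.

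Phase length acts separately. At a constant event rate, expected recorded events scale with capture × length. For a start at 238 h the length ratio is 298.5/238 = 1.25, and the product is 1.25 × (0.71 to 0.94) = 0.89 to 1.18. For a start at 166 h it is 298.5/166 = 1.80, and 1.80 × (0.61 to 0.86) = 1.10 to 1.55.

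**The case against.** A reader might infer from 9 questionings against 3 that AE frequencies must rise under BI 730357 through the schedule alone. The documents do not support that:

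- AEs are recorded throughout both periods, subjects must volunteer them with onset times, and the scheduled questions are only a minimum. An event first mentioned at 71, 95 or 143 h is still recorded and assigned by onset. With complete recall the schedule adds nothing.
- The window from 48 to 143 h is not an analysis phase. Over the phases actually tabulated, the same recall model can favour either treatment.
- Counting subjects rather than events means that repeat reports add nothing.
- The twice-daily questions before the Test cocktail do not enter 'BI + Cocktail'.

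It is also fair to say that safety is descriptive with no hypothesis testing, that questioning at dosing visits is a by-product of supervised dosing, and that the fixed sequence confounds any AE contrast with period.

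All of this stands, and it limits the point to a possible bias. It does not remove it: spontaneous reporting applies equally in both periods and so does not balance the prompting, and the SAP has neither an equal window nor a warning.

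**Conclusion.** The imbalance is a matter of count: 10 against 14 questionings from 0 to 48 h, 3 against 9 (7 visits) from after 48 h to 143 h, then long unasked stretches, in phases of at most 240 h and up to about 298.5 h. What follows for the AE tables is a possible ascertainment bias whose size and direction the documents do not fix. The capture ratios (1.06 to 1.26 for 48 to 143 h, about 0.6 to 1.3 for whole phases, at most 1.02 for 0 to 48 h) rest on assumed recall half-lives, uniform onset and, for whole phases, an assumed interval between periods. They show that the phase comparison is sensitive to the schedule and that the first 48 h is nearly immune. They do not predict a result. The point is minor: PK endpoints are untouched, and only the reading of descriptive AE frequencies is affected.

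**What to change.** In SAP 7.8.1, add a supplementary table of subjects with AEs with onset from 0 to 48 h after each cocktail dose, by treatment, SOC and preferred term, as a supportive Test versus Reference comparison. That window has equal length, is in-house in both periods and has near-matched questioning. Keep the full phase tables as planned, with a footnote such as: *Phase length and the frequency of scheduled AE questioning differ between phases; differences in frequency between columns may partly reflect this.*

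The table should not replace the phase tables or bar discussion of later events. It does not remove the period confounding of the fixed sequence, and 10 against 14 questionings is close but not identical.

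Cost: one extra table and one footnote, from data already collected, with no change to visits or procedures. The downside is that later-onset events appear only in the full phase tables.
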